## 5.1. Adverse Events

The analysis of AEs will be based on the MedDRA coded terms as provided in the clinical database.

### 5.1.1. Definitions

Solicited AEs shown in the tables are extracted from the diary pages of the CRF. For unsolicited AEs, only the AEs within the 28-day period following each vaccination will be presented in the safety tables except for SAE and AESI (AE of special interest), which will be captured and tabulated in the outputs covering the whole study period. All other collected unsolicited adverse events will be presented through listings.

Solicited local AEs will be by definition considered as related to the study vaccine.

The severity of the AEs will be classified as grade 1 to 4. Solicited events that are graded less than grade 1, are not considered as AE. In case no grades are available, the grading of the solicited events will occur according to the grading list in attachment 1 of the CTP.

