2. OBJECTIVES, ENDPOINTS, AND HYPOTHESIS

2.1. Objectives and Endpoints

Objectives		Endpoints		
Primary		_		
To assess safety/tolerability of the differe vaccine regimens	nt •	Solicited local and systemic adverse events (AEs) for 7 days after each vaccination.		
	•	AEs for 28 days after each vaccination.		
	•	Discontinuations from vaccination/from study due to AEs.		
	•	Serious adverse events (SAEs) and AEs of special interest (AESIs) of confirmed HIV infection during the course of the study, including the LTE phase.		

Objectives	Endpoints
• To assess Envelope (Env)-binding antibody (Ab) responses of the 2 different vaccine regimens.	Env-specific binding Abs (titers and breadth).
To assess safety/tolerability of a late boost vaccination.	Solicited local and systemic AEs for 7 days after the late boost vaccination.
	• AEs for 28 days after each the late boost vaccination.
	 SAEs and AESIs of confirmed HIV infection until the end of the study.
	AESIs of TTS for 6 months after the late boost vaccination
Secondary (applicable to main study, LTE and late	boost vaccination)
• To assess neutralizing Ab (nAb) responses,	• Env-specific nAbs (titers and breadth)
Ab functionality (as assessed by phagocytosis), and Ab isotyping.	• Env-specific functional Abs (phagocytosis score and breadth).
	• Env-specific binding Ab isotypes (immunoglobulin (Ig)A, IgG1-4) (titers and breadth).
To assess T-cell responses.	 Interferon gamma (IFNγ) peripheral blood mononuclear cell (PBMC) responders to mosaic and potential T-cell epitopes (PTE) peptide pools of Env/group-specific antigen (Gag)/polymerase (Pol).
	 Cluster of differentiation (CD)4+ and CD8+ T-cell functionality (% cells producing ia, IFNγ, interleukin 2 (IL-2), IL-4, tumor necrosis factor α [TNFα]).
	 T-cell development with emphasis on follicular helper T- cells and memory differentiation.^d
Exploratory (applicable to main study, LTE and lat	e boost vaccination)
• To explore whether the adenovirus serotype 26 (Ad26) vector is shed after vaccination.	 Polymerase chain reaction (PCR) positive for Ad26 sequences (urine and mid-turbinate swab).
To explore Ab functionality (other than phagocytosis).	• Ab functionality evaluation (such as Ab-dependent cellular cytotoxicity [ADCC], Ab-dependent complement deposition [ADCD]; excluding phagocytosis (ie, Ab-dependent cellular phagocytosis [ADCP]).
• To explore Ab Fc characterization.	• Ab Fc (sub)typing.

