10.2. Discontinuation of Study Treatment/Withdrawal from the Study

Discontinuation of Study Treatment

Subjects will be withdrawn from study vaccine administration during the main study for the reasons listed below. These subjects must not receive any additional dose of study vaccine but should enter the follow-up phase with assessments of safety and immunogenicity. The subject will be encouraged to complete the post-vaccination follow-up visits of the last vaccination received and a 12 and 24 weeks follow-up visit after the last vaccination received, specified as Week 60 and Week 72 in the TIME AND EVENTS SCHEDULE. Additional unscheduled visits may be performed for safety/tolerability reasons, if needed. In case the subject withdraws before receiving the first vaccination, the subject is not required to attend follow-up visits. In case of questions, the investigator is encouraged to contact the study responsible physician. Subjects who have been prematurely withdrawn from study vaccine administration are not eligible for the LTE phase.

- Unblinding
- Anaphylactic reaction following vaccination
- Pregnancy
- Any related SAE
- Any related AE, worsening of health status or intercurrent illnesses that, in the opinion of the investigator, requires discontinuation from study vaccine
- Confirmed HIV infection
- Chronic or recurrent use of immunosuppressants (after discussion with the sponsor)

• Missing more than 1 study vaccination

Withdrawal From the Study

Each subject has the right to withdraw from the study at any time for any reason without affecting the right to treatment by the investigator. The investigator should make an attempt to contact subjects who did not return for scheduled visits or follow-up. Although the subject is not obliged to give reason(s) for withdrawing prematurely, the investigator should make a reasonable effort to ascertain the reason(s) while fully respecting the subject's rights.

A subject will be withdrawn from the study for any of the following reasons:

- Lost to follow-up
- Withdrawal of consent
- Death
- Repeated failure to comply with protocol requirements
- Decision by the sponsor or the investigator to stop or cancel the study
- Decision by local regulatory authorities or IRB/IEC to stop or cancel the study

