12.3. Procedures

12.3.1. All AEs

All AEs and situations requiring special notification (see Section 12.2) will be reported from the time the signed and dated study-specific ICF is obtained until 28 days (including relevant visit window, if applicable) after first dose of study vaccine, and thereafter, pre-dose on the day of injection and for 28 days (including relevant visit window, if applicable) after each subsequent dose of study vaccine. Unsolicited AEs with the onset date outside the timeframe defined above (>28 days after previous study vaccination), which are ongoing on the day of the subsequent vaccination, should be recorded on the CRF AE page.

All SAEs and AEs leading to discontinuation from the study vaccination (regardless of the causal relationship) and AESIs of confirmed HIV infection are to be reported for the duration of the study. The sponsor will evaluate any safety information that is spontaneously reported by an investigator beyond the time frame specified in the protocol.

From the time of local regulatory approval of protocol amendment 5 onwards, TTS is considered to be an AESI. Thrombotic events and/or thrombocytopenia are considered to be potential AESIs. Thrombocytopenia is defined as platelet count below the LLN range for the testing lab. All AESIs, including potential AESIs, will be reported to the sponsor from the moment of the late boost vaccination until 6 months after the late boost vaccination. Each potential AESI will be reviewed to identify a TTS case.

All events that meet the definition of an SAE will be reported as SAEs, regardless of whether they are protocol-specific assessments.

The investigator will monitor and analyze study data including all AE and laboratory data as they become available and will make determinations regarding the severity of the adverse experiences and their relation to study vaccine. AEs will be deemed either related to study vaccine or not related to study vaccine, according to Section 12.1.2. To ensure that all AEs are captured in a timely manner, CRFs will be entered in real-time, and subjected to review to identify AEs which may invoke study pausing rules.

The investigator or designee must review both collected solicited events and other AE CRFs to insure prompt and complete identification of all events that require expedited reporting as SAEs, invoke study pausing rules or are other serious and unexpected events.

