**NOTE:**

a The start time of screening phase is 00:00. In case an earlier date is available (e.g. for lab or vital signs then use the very first date in order to include all data)

b In case a dose is not administered, the observations end up in the previous Follow-Up phase

For the immunogenicity analyses no phases will be constructed.

The periods/phases will be used primarily for safety and concomitant medication allocation. The post-dose periods (and the regimen phase) are considered active periods/phase, the screening and follow-up phases are considered non-active phases.

For descriptive statistics over time, assessments (regardless of the investigated parameter) will be allocated to an analysis visit based on the visit number as captured in the database.

For subjects that received a first dose, but did not receive a 2nd dose while still continuing their planned visit schedule, the measurements after the planned but not administered 2nd dose will not be included in graphs and tables showing descriptive statistics over time. Those measurements will be shown in listings but it will be indicated that these are not used in the analysis. Moreover, the vaccinations done after a missed one will not be shifted to the previous one but will be considered as planned: in the example above if the 2nd is missed, the 3rd vaccination will still be reported as post-dose 3.

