### 5. SAFETY

The safety and tolerability endpoints are:

- Unsolicited AEs 28 days following each vaccination
- Solicited local and systemic AEs (reactogenicity), collected daily from day of vaccination for 7 days post-vaccination (day of vaccination and the subsequent 7 days).

The safety and tolerability analysis will be performed on the FA set. Specifically, the analysis for solicited adverse events will be done on those subjects in the FA set for whom reactogenicity assessments are available in the database (either via on-site assessments or via the diary pages of the CRF).

Safety data will be tabulated per period by regimen. Only the active periods will be shown in the tables (AE, Lab, VS), except for SAEs. In addition, for a selection of tables (AE, Lab), tabulations per subject by vaccine and per dose by vaccine will be provided.

For the subject receiving the late boost vaccination, the AEs will be tabulated as follows:

- Reporting only the late boost period (post-dose 5) for the 2 LB regimens (LB Tetravalent Clade C-Mos and LB Placebo)
- Reporting all post doses (post-dose 1,2,3,4,5) for the vaccine they received (Any post-dose will not be included).

In the ‘per subject by vaccine’ analysis, the safety will be presented per periods (post-dose 1, 2, 3, 4) by vaccine rather than by regimen. A ‘post any dose’ period (= regimen phase in section 2.1) will be added, that summarizes the safety after all administered doses of a vaccine. The post-any-dose period allows determining how many subjects reported events after administration of a certain vaccine regardless the number of doses. Each subject is counted only once. In case a subject has the same event after more than one dose, it is counted only once (and in case of showing attributes, the worst corresponding attribute is shown) in the post-any dose period. The denominator is the number of subjects that received the considered vaccine in the considered period.

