### 5.1.2. Analysis of Adverse Events

Number and percentage of subjects with at least one particular AE (unsolicited/solicited) will be tabulated. Unsolicited AEs will be summarized by System Organ Class and Preferred Term. Solicited AEs will be summarized by class (local, systemic) and preferred term.

For solicited AEs following tables will be provided: summary, by worst severity grade, grade 3, related (systemic only), time to onset (in days) and duration (in days) for most frequent events and body temperature. Note: Duration is defined as number of days from the start of the event until resolution of the event. The time to first onset is defined as (date of first onset – reference date + 1). The reference date is the start date of the vaccination period.

For unsolicited AEs following tables will be provided: summary table (including SAE, fatal outcome, AESI and discontinuation), all events, most frequent, grade 3, permanent stop of vaccine, related, SAE and AESI.

Listings and/or subject narratives will be provided as appropriate, for those subjects who die, discontinue study vaccinations due to an AE, or experience a severe or serious AE.

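### Non-serious AEs that stop vaccination but start between the post-dose windows are left out of the SAP's AE tables, although AE-related discontinuation is a primary endpoint

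*SAP*

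**What the plan says.** Protocol 2.1 lists "Discontinuations from vaccination/from study due to AEs" among the primary safety endpoints. It stands as its own item beside the 28-day AE endpoint and carries no time limit.

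The collection rule in Protocol 12.3.1 covers "All SAEs and AEs leading to discontinuation from the study vaccination (regardless of the causal relationship", and makes these reportable for the duration of the study. Protocol 10.2 allows a related non-serious AE, or an intercurrent illness, to end vaccination at the investigator's judgement. This reason is listed separately from a related SAE.

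The SAP restricts what is tabled in two places:

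- SAP 5: "Only the active periods will be shown in the tables (AE, Lab, VS), except for SAEs".
- SAP 5.1.1: "only the AEs within the 28-day period following each vaccination will be presented in the safety tables except for SAE and AESI". It adds: "All other collected unsolicited adverse events will be presented through listings".

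The notes to the phase table in SAP 2.1 say that "the screening and follow-up phases are considered non-active phases". SAP 5.1.3 allocates an AE to a period by its start date and time.

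The unsolicited-AE tables planned in SAP 5.1.2 end with "permanent stop of vaccine, related, SAE and AESI", and the AE summary table includes discontinuation. No text exempts either output from the restriction. The endpoint list that opens SAP 5 names 28-day unsolicited AEs and 7-day solicited AEs, but not discontinuations.

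**The concern.** The protocol collects vaccine-stopping AEs beyond 28 days, and it makes the resulting discontinuations a primary endpoint. The SAP then applies to the matching AE table a window meant for ordinary unsolicited AEs, and exempts only SAEs and AESIs. An AE that is neither, but that begins between windows and leads the investigator to withhold the next dose, meets the endpoint and is missing from its AE table.

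The gap is a realistic one. Protocol 1.1.2.2 reports that the Week 72 analysis of this study found no SAEs and no AESIs, but a few AEs leading to discontinuation. Those AEs were therefore non-serious, and the SAE/AESI exception could rescue none of them. The documents do not say whether any of them began outside a window.

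At stake is whether a reader can take the count, term, grade and relatedness of vaccine-stopping AEs from the AE tables, and whether that count matches the disposition table.

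**Working it through.** The documents state no figure for this point, so there is none to reproduce. The check follows the rules for one case and then measures the time they exclude.

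**One case through the rules.** Take a non-serious AE, related in the investigator's view, that starts in Week 34 and causes dose 4 (Week 48) to be withheld.

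1. Collected? Yes. Protocol 12.3.1 applies for the whole study, and Visit 12 (Day 253) records AEs leading to treatment discontinuation.
2. Period? Dose 3 is planned for Day 169 and its active period ends about four weeks later, near Week 28. A Week 34 start falls in Follow-Up 3.
3. Tabled? Follow-Up 3 is non-active, and the AE is neither an SAE nor an AESI. It goes to listings only.
4. Result: absent from the permanent-stop table and from the summary's discontinuation line.

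**Share of inter-dose time outside the windows.**

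- Planned dose days (Protocol 9.1.2): 1, 85, 169, 337.
- Gaps: 85 − 1 = 84; 169 − 85 = 84; 337 − 169 = 168. Total 336 days.
- Active period (SAP 2.1): 28 days, or to the 4-week visit if later. That visit has a window of ±5 days, so up to 33 days.
- Formula: sum of (gap − window) ÷ sum of gaps.

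| Window | After dose 1 | After dose 2 | After dose 3 | Outside | Share |
|---|---|---|---|---|---|
| 28 days | 56 | 56 | 140 | 252 of 336 | 75% |
| 33 days | 51 | 51 | 135 | 237 of 336 | 71% |

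Counting the day of vaccination itself as covered lowers each share by about one percentage point (249 and 234 of 336).

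**What one missing case would do (assumed count).** The one-sided 95% upper bound for 0 of n is 1 − 0.05^(1/n): 11.3% for n = 25 and 2.95% for n = 100. This agrees with the bounds of under 12% and under 3% in Protocol 11.3. For 1 of n, the bound solves (1 − p)^n + n·p·(1 − p)^(n−1) = 0.05: 17.6% for n = 25 and 4.66% for n = 100. If one subject had such an event, the table would show:

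- Group 2: 0/100 (bound 2.95%) instead of 1/100 (4.66%).
- Group 1: 0/25 (11.3%) instead of 1/25 (17.6%).

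**What stays in the tables.** Only onset matters. An AE that starts inside a window and stops vaccination later is tabled. So is a continuing event of the same preferred term that starts in an active and then a non-active period (SAP 5.1.3, Step 2, rule 3). An AE with a partial start date may also match an active period.

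**The case against.** The strongest reply is that the endpoint is a count of subjects, and that count is still tabled. SAP 4.2 tabulates discontinuation, with reasons, both from further vaccination and from the trial, without any onset window. SAP 5.1.2 adds listings and/or narratives for subjects who stop vaccination because of an AE, and Protocol 11.5 permits summaries for them. This stands. A reader might infer that a primary endpoint goes unreported or that events are hidden, but the documents do not support that. What the reply does not restore is a tabulation by term, grade, relatedness and post-dose period. Nor does it prevent the AE and disposition tables from disagreeing if such an event occurs.

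Three further inferences also fail:

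- **That about 75% of vaccine-stopping AEs are lost.** The 75% is calendar time. Turning it into events needs an onset distribution that the documents do not give.
- **That the lost events chiefly concern the first-in-human antigen.** Mosaic gp140 starts at Week 24 and only in Group 2. Of the 36 uncovered weeks (8 + 8 + 20), 16 (44%) come before it.
- **That Protocol 10.2 needs an AE withdrawal reason.** That list opens with "A subject will be withdrawn from the study for any of the following reasons", so it sets mandatory withdrawals. An AE entry would read as compulsory and would conflict with the same section, which keeps subjects who stop vaccination in follow-up. Exit visits record any AEs (Protocol 9.1.7 and 9.1.10), although a subject may decline the visit. The CRF is not among the documents, so its reason codes cannot be judged.

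There is also a point on timing. SAP 1 says outputs for data up to Week 72 will not be repeated, and no study dose follows the late boost. A wording change alone would therefore leave the main-study tables as they are. This is correct and belongs in the cost.

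**Conclusion.** The point holds as a defect in the SAP's table-inclusion rule. A non-serious AE that starts in Follow-Up 1, 2 or 3 and stops vaccination is collected, but it is missing from the two AE outputs meant to show it. The excluded span is 71–75% of planned dose 1 to dose 4 time, assuming doses on their planned days and active periods of 28 to 33 days. The number of events affected is unknown and may be zero.

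The loss is AE-level tabulation and assured consistency with the disposition table, not the subject count. Two related mismatches belong with it. SAP 5 exempts SAEs only, while SAP 5.1.1 exempts SAEs and AESIs. And the endpoint in Protocol 2.1 includes discontinuation from the study, while the extended collection rule in Protocol 12.3.1 names only discontinuation of vaccination.

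**What to change.** In the SAP:

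1. In Sections 5 and 5.1.1, extend the whole-study exception to AEs leading to permanent stop of vaccine and to any recorded AE leading to discontinuation from the study.
2. Table these AEs over the whole study, by the last dose received before onset, with term, grade and relatedness. Use the same scope for the discontinuation line of the AE summary.
3. Add AE-related discontinuation to the endpoint list that opens Section 5.
4. Make the exceptions in Sections 5 and 5.1.1 identical, covering both SAEs and AESIs.

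In the protocol, reconcile the study-discontinuation half of the endpoint in 2.1 with the collection wording in 12.3.1. Leave the withdrawal list in 10.2 unchanged.

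Cost: a few sentences in the SAP, a short protocol clarification, and one added or re-run main-study output, since Week 72 outputs are not otherwise repeated. AEs leading to discontinuation of vaccination are already collected for the whole study, so that part needs no new data.

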- ¹¹ Solicited local and systemic signs and symptoms will be recorded by the subject in the diary and solicited local and systemic AEs recorded in the CRF for 7 days after boost vaccination; unsolicited AEs will be recorded from signing of ICF addendum for boost vaccination onwards until 28 days after boost vaccination; SAEs and AESIs of confirmed HIV infection will be recorded from signing of the initial ICF of the main study onwards until the end of the study. Applicable from the time of local regulatory approval of protocol amendment 5 onwards: AESIs of TTS (including potential AESIs) are to be reported to the sponsor until 6 months after the late boost vaccination. In case of a potential AESI of TTS, a serum sample should be obtained to test for anti-PF4 at the local laboratory or substitute local laboratory, if possible; repeat testing may be requested for confirmation upon sponsor discretion. A test for anti-PF4 will also be performed on a stored pre-vaccination sample, if possible.
- ¹² Observation at the study site for at least 30 minutes for presence of any acute reactions and solicited events.
- ¹³ In case the diary was not completed (7 days post-boost) at the time of Visit 22b.
- ¹⁴ Approximately 6 months post Visit 24, the investigator or study-site personnel will have a (remote) follow-up communication with subjects consenting to the 24-month follow-up (by email, telephone, or visit; according to the subject's preference) to collect information on occurrence of any SAEs.
- 15 Visit 25 is an optional visit. Visit 24 and Visit 25 will be the final visit for subjects who, respectively, do not consent and subjects who consent to the 24-month follow-up.
- ¹⁶ For those subjects who are unable to continue participation in the study, an exit visit will be conducted as soon as possible.
- ¹⁷ If a visit can't be scheduled within the allowed window, it will be assessed on a case-by-case basis upon discussion between the investigator and the sponsor whether this visit can still be performed. Note that 1 month should be interpreted as 30 days and 1 week as 7 days; hence, the visit window for visit 22a ought to be interpreted as -28 days/+120 days.

ABBREVIATIONS AND DEFINITIONS

Ab antibody Ad adenovirus

Ad5 adenovirus serotype 5 Ad26 adenovirus serotype 26

ADCC antibody-dependent cellular cytotoxicity
ADCD antibody-dependent complement deposition
ADCP antibody-dependent cellular phagocytosis

AE adverse event

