9.3. Safety Evaluations

Details regarding the PSRT and DRC are provided in Section 11.7 and 11.8, respectively.

Any clinically significant abnormalities that are considered related to vaccination persisting at the end of the study/early withdrawal will be followed by the investigator until resolution or until a clinically stable endpoint is reached (see Section 12.3.2).

The study will include the following evaluations of safety and tolerability according to the time points provided in the TIME AND EVENTS SCHEDULE.

AEs

All AEs will be reported from the time the signed and dated study-specific ICF is obtained until 28 days after first dose of study vaccine, and thereafter, pre-dose on the day of injection and for 28 days after each subsequent dose of study vaccine. Unsolicited AEs with the onset date outside the timeframe defined above (>28 days after previous study vaccination), which are ongoing on the day of the subsequent vaccination, should be recorded on the CRF AE page. All SAEs and AEs leading to discontinuation from the study vaccination and AESIs of confirmed HIV infection are to be reported from signing of study-specific ICF onwards for the duration of the study (see Section 12.3.1 for details). Adverse events will be followed by the investigator as specified in

Section 12.1.3. From the time of local regulatory approval of protocol amendment 5 onwards, TTS is considered to be an AESI. Thrombotic events and/or thrombocytopenia are considered to be potential AESIs. Thrombocytopenia is defined as platelet count below the LLN range for the testing lab. All AESIs of TTS, including potential AESIs, will be reported to the sponsor from the moment of the late boost vaccination until 6 months after the late boost vaccination. Each potential AESI will be reviewed to identify a TTS case.

For solicited AEs, the following applies.

Solicited AEs

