## **2.3. Analysis Sets**

### **2.3.1. Full Analysis Set**

The Full Analysis Set (FA) will consist of all subjects who were randomized and who received at least one dose of study vaccine. This will be the primary population for all analyses (except immunogenicity, see below) described in this document.

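### No planned SAP output matches the primary late-boost endpoint of TTS over 6 months: one table stops at about 28 days, the other is not limited to boosted subjects or split by arm

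*SAP*

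**What the plan says.** **Protocol.** Section 2.1 lists TTS over the 6 months after the late boost among the primary endpoints for late-boost safety. Section 9.3 states that TTS events, including potential ones, "will be reported to the sponsor from the moment of the late boost vaccination until 6 months after the late boost vaccination". Section 12.3.1 adds a calendar limit: "From the time of local regulatory approval of protocol amendment 5 onwards, TTS is considered to be an AESI". Footnote 11 of the Time and Events Schedule for the late boost extension repeats both limits. The other AESI has a different span: under Section 12.3.1, "AESIs of confirmed HIV infection are to be reported for the duration of the study".

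**SAP.** The Introduction says that the plan covers data to the end of the study and exists to add the late-boost and long-term extension analyses. TTS is not mentioned anywhere in it.

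- Section 5: "The safety and tolerability analysis will be performed on the FA set". Section 2.3.1 defines that set as "all subjects who were randomized and who received at least one dose of study vaccine". Section 5 also limits AE tables to active periods, with SAEs the only named exception. For boosted subjects it adds two displays: post-dose 5 alone for the two late-boost regimens, and post-doses 1 to 5.
- Section 5.1.1 limits unsolicited AE tables to 28 days after each vaccination, "except for SAE and AESI (AE of special interest), which will be captured and tabulated in the outputs covering the whole study period". Section 5.1.2 lists AESI as one of the unsolicited AE tables.
- Section 2.1, Table 3: post-dose 5 ends at 28 days or at the scheduled 4-week visit if that is later (or at last contact, if earlier). Follow-Up 5 comes next, and the notes to the table class follow-up phases as non-active.

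**The concern.** The two AESIs have different risk sets. Confirmed HIV infection is collected in everyone from consent to the end of the study, so a whole-study table on the Full Analysis Set suits it. TTS is reportable as an AESI only in late-boost recipients, only for 6 months, and only once Amendment 5 is locally approved. The SAP has a single AESI category and no rule for that narrower risk set.

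A primary endpoint is at stake. A low or zero TTS count in the by-arm table could be read as covering 6 months when it covers about 4 weeks. Protocol Section 1.1.2.3 puts usual symptom onset at 1 to 4 weeks and sometimes later, up to 42 days, so the cut falls inside the period of interest. A low or zero percentage in the whole-study output could be read as applying to every vaccinated subject, and it would not set active boost against placebo boost.

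**Working it through.** **1. The plan's own zero-event figures.** Protocol Section 11.3 gives 95% bounds for zero observed events. The formula 1 − 0.05^(1/n) gives 11.29% for n = 25 (stated as below 12%) and 2.95% for n = 100 (stated as below 3%). Both reproduce. The plan states no figure for TTS.

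**2. Time covered by the by-arm table.** The late-boost schedule defines a month as 30 days, so the window is 6 × 30 = 180 days.
- Post-dose 5 ending at day 28: 28/180 = 15.6%.
- Post-dose 5 ending at a 4-week visit held at the end of its ±2-week window: (28 + 14)/180 = 23.3%.

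The rest of the window lies in Follow-Up 5. The second late-boost display (post-doses 1 to 5) ends at the same point.

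**3. Subjects in the whole-study output, if computed on the Full Analysis Set.** Inputs: planned 25 + 100 + 25 = 150 (Protocol Section 3.1); at least 48 boosted, allocated 3:1, so 36 active and 12 placebo.
- Share of the set ever under TTS reporting: 48/150 = 32%. Dilution: 150/48 = 3.1-fold.
- One case: 1/150 = 0.67%; 1/48 = 2.08%; 1/36 = 2.78%.
- Zero cases, same formula as step 1: 1.98% (n = 150), 6.05% (n = 48), 7.98% (n = 36).

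Sensitivity:
- Only Groups 1 and 2 counted: 125/48 = 2.6-fold, one case 1/125 = 0.80%.
- 75 boosted: 150/75 = 2.0-fold.
- 112 boosted (assumption: all 125 active subjects less about 10%): 150/112 = 1.3-fold.

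**4. The two outputs against the endpoint.**

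| | Late-boost table by arm | Whole-study AESI output |
|---|---|---|
| Boosted subjects only | yes | not stated; Full Analysis Set by default |
| Reaches 6 months | no | yes |
| Split by late-boost arm | yes | not stated |
| TTS handled apart from HIV infection | not stated | no, one AESI category |

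**5. Section 5 against Section 5.1.1.** Take a non-serious platelet count below the lower limit of normal 60 days after the boost. Protocol Section 12.3.3.2 makes it a potential TTS case. SAP Section 2.1 places it in Follow-Up 5, a non-active phase. Under SAP Section 5 it is not an SAE, so it enters no table. Under SAP Section 5.1.1 an AESI is tabulated for the whole study, so it does, provided that a potential AESI counts as an AESI, which the SAP does not say. The two rules give opposite answers.

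**The case against.** The strongest reply is that the Full Analysis Set is an analysis set and not a stated TTS denominator. SAP Section 5 tabulates safety per period, gives boosted subjects their own tables by arm, and for the per-subject-by-vaccine analysis uses as denominator the recipients of that vaccine in that period. Only boosted subjects can enter post-dose 5. The SAP Introduction says that outputs up to Week 72 will not be repeated, and Group 3 cannot enter the extension, which argues against a table of 150. The 48 is a floor. Safety is descriptive, so the bounds above illustrate scale and are not planned outputs. Summaries by preferred term would also put TTS on its own line.

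Much of this stands, and it rules out two stronger readings.

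- A reader might infer that the TTS denominator consists mostly of subjects who were never observed. The documents do not support that. No section fixes the denominator at 150, and the word mostly would need fewer than 75 boosted. Serious thrombotic events are collected as SAEs in everyone throughout, and all AEs are collected for 28 days after the boost.
- A reader might infer that TTS was missed in subjects boosted before Amendment 5 was locally approved. The dates make such boosts possible: Amendment 3, which introduced the boost, is dated 6 Feb 2020 and Amendment 5 is dated 21 May 2021. But no boost or approval dates are given, so the number could be zero. Such subjects would lack special-interest reporting and non-serious events after about day 28; they would not lack all safety data.

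The reply does not supply a matching output. The quoted denominator rule belongs to an analysis whose listed periods are post-doses 1 to 4. The Late Boost Analysis Set (SAP Section 2.3.3) is a subset of the per-protocol immunogenicity set, so it is not a safety set. A preferred-term line changes neither the denominator nor the arms.

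**Conclusion.** The point holds. Followed as written, the SAP gives no output that reports TTS in late-boost recipients, by late-boost arm, over the 6 months named in the primary endpoint. The by-arm table covers about 16% of the window (about 23% with a late 4-week visit). The whole-study AESI output covers the window in an unspecified population without the late-boost split. If that population is the Full Analysis Set, the percentage is diluted about 3-fold at the planned minimum, and less if more subjects are boosted.

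The conflict between SAP Sections 5 and 5.1.1 depends on none of these numbers: it decides whether a non-serious potential TTS event after post-dose 5 is tabulated at all. The dilution figures rest on planned numbers and on the default analysis set. The number boosted before local approval is unknown, and no size is attached to it here. The change should be made, since the endpoint is primary and the correction is small.

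**What to change.** 1. Split the AESI output. Keep confirmed HIV infection on the Full Analysis Set over the whole study.
2. Add one table of TTS and potential TTS in late-boost recipients only, by late-boost arm, from the boost to 6 months after it or last contact, with boosted subjects as denominator. At the late-boost interim, about 4 weeks after the last boost, state how many have completed the 6 months.
3. Reconcile SAP Section 5 with Section 5.1.1 so that AESIs in Follow-Up 5 are tabulated, and say that potential AESIs are included.
4. If any boosts preceded local approval of Amendment 5, flag those subjects. Search their recorded AEs (to about day 28) and SAEs with the Attachment 5 terms and thrombocytopenia terms, and show what is found on a separate line.

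The cost is SAP wording and one table. Item 4 also needs the approval date for each site and one term search of existing data. Any rate or bound derived from the new table will look less favourable than one on the Full Analysis Set, because it rests on fewer subjects.
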